### **13. Costs to the Subject:**

The study will be at no additional cost to the subject on top of his regular hospitalization for heart failure and elective catheterization.

### **14. Data Analysis & Statistical Considerations:**

Descriptive statistics of continuous outcomes will include sample size, mean, median, standard deviation, minimum and maximum. For categorical outcomes, the number and percentage of subjects in each category will be presented. Statistical comparisons will be made using t-tests for continuous outcomes and chi square or Fisher's exact test (depending on overall event rates) for categorical outcomes. Paired t-tests will be used to compare changes from baseline to post-intervention. All statistical analyses will be performed using SAS for Windows (version 8.2 or higher) or other widely accepted statistical or graphical software. Subject data listings and tabular and graphical presentations of results will be provided. Unless otherwise specified, a two-sided 0.05 level of significance will be used to declare change in pre- and post-procedure variables different.

For power analysis, our primary endpoint is decreased in central venous pressure following nerve blockade. Based on preliminary animal experiments, we anticipate a reduction of CVP of 25%. For a sample size of 16, If the true difference in the experimental and control means is 25%, we will be able to reject the null hypothesis that the population means of the experimental and control groups are equal with probability (power) .90. The Type I error probability associated with this test of this null hypothesis is 0.05.

There is no direct measure of technical success following attempted block of the splanchnic nerves. The location of the splanchnic nerves is estimated biased on human anatomy dissections and established nerve block protocols used by the anesthesiology department. Procedural success to block the splanchnic nerves will be assumed in 70% of the cases based on the experience in splanchnic nerve blocks in subjects with intractable cancer.

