#### **4. Design & Procedures:**

This study will be a prospective, uncontrolled clinical trial. The study will not be controlled as invasive monitoring of hemodynamics will be performed, allowing clear demonstration of a cause-effect relationship.

This study aims to piggy-back on an elective right heart catheterization (RHC) in subjects with chronic heart failure. The right heart catheterization will be part of the subject's standard of clinical care (SOC). Subjects eligible for this study will be referred to the Duke cath lab for the evaluation of cardiac filling pressures because it is found to be necessary by the outpatient provider. This will occur in the cardiac catheterization lab. Subjects get scheduled for RHC days to weeks (2-3) ahead of their procedure. The eligible subject will be contacted before the study to be informed about the eligibility for the study and basic information about the study will be provided over the phone shortly after they have been scheduled. Subject will be consented in person in the morning of the procedure.

The subject will undergo pre procedural testing as demonstrated below in the flow chart (all part of the clinical study - CS). Besides the RHC (SOC) the subject will undergo an invasive cardiopulmonary exercise with the RHC in place. Baseline evaluation is followed by a regional nerve block (bilateral splanchnic nerves) while the subject is in the catheterization lab. This will be performed by an anesthesiologist experienced in splanchnic nerve blocks.

Figure 2: Study flow chart

[figure not shown]

Table: Study events

Required Assessment	Pre procedure (day of)	Baseline (intra-procedure)	Block	Post Block Procedure	Recovery	24 h after procedure	48 h after procedure	6 Months after Procedure (±14 days)
Vitals (BP, HR, RR, SpO2)	X (SOC)	X (SOC)	X (SOC)	X (SOC)	X (SOC)			
Weight	X (SOC)				X (SOC)			
Orthostatic vitals	X (CS)				X (CS)			
Urine output (continuous recording)	X (CS)	X (CS)	X (CS)	X (CS)	X (CS)			
Valsalva		X (CS)		X (CS)				
Labs: BMP, pro-BNP, urine sodium,	X (SOC/CS)				X (CS)			
Labs (Angiotensin II), Plasma Metanephrines, Vasopressin, Plasma Catecholamines, Lactate		X (CS)		X (CS)				
Dyspnea Questionnaire		X (CS)		X (CS)	X (CS)	X (CS)	X (CS)	
Six minute walk test	X (CS)				X (CS)			
Impedance and lung fluid content measurement		X (CS)		X (CS)				
Heart rate variability	X (CS)	X (CS)	X (CS)	X (CS)	X (CS)			
Echocardiogram		X (CS)		X (CS)				
Invasive CPX		X (SOC/CS)		X (CS)				

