Splanchnic nerve block			X (CS)					
Phone Call						X (CS)	X (CS)	X (CS)

\*Phone call will capture mortality status and number of subject admissions to the hospital since procedure

Following enrollment into the study the subject will undergo the following tests/measurements. A majority of the clinical testing occurs as part of the clinical study (CS) however the main procedure of RHC is standard of care (SOC).

Pre-procedure: Following information will be collected from the subject's charts that will be done as standard of care (SOC). Study specific tests/recordings are also listed below:

- If the subject is female and childbearing potential and has not had a pregnancy test since the arrival to the hospital, a blood pregnancy test will be done (CS). If positive the subject will be excluded from the study.
- Subjects will have strict measurement of urine output (SOC). A urine sample will be sent to the laboratory to check for the sodium concentration (CS). Subjects requiring a foley catheter will have measurements taken at comparable time intervals (SOC).
- Recorded vitals including weight, BP, HR, RR, SPO2 on the day before procedure and within 1h before procedure (SOC) and record heart rate variability using a non-invasive wrist monitor for 5 minutes (CS).
- Orthostatic vitals (5 minutes supine, 1+5 minutes sitting and 1+5 minutes standing) on the day before procedure and within 1h before procedure (CS). Also we will document whether s has symptoms bending over for 10 seconds (bendopnea).
- Labs: Basic metabolic panel (BMP) (SOC), brain natriuretic peptide (BNP) (CS), urine sodium (CS) plasma angiotensin II (CS), plasma arginine vasopressin (CS), plasma catecholamines. This will not require an extra lab draw. Total expected blood loss is <20ml.
- Dyspnea questionnaire using a 7-point Likert scale and Visual Analog Scale (CS)
- Six minute walk test (CS)
- Echocardiogram at baseline and after the block will be performed while the subject is on the cath table (CS). This is considered one continuous echo. This ultrasound test will also be used to look at liver blood flow.
- If the subject is on diuretics medications the scheduling of the medication will be adjusted to minimize interference with the study intervention.

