Before cardiopulmonary exercise begins, the subject will perform the Valsalva maneuver. The subject will sit up on the catheterization lab table, after the intravenous lines have been placed. The subject will have an empty syringe placed in their mouth. He/she will blow into the syringe for 30 seconds. This is the standardized method for performing the Valsalva maneuver (Saxena, M, Journal of American Heart Association, 2018). The intracardiac pressures will be measured continuously during the 30 seconds. Following the Valsalva maneuver, the subject will be placed supine on the stationary bike for cardiopulmonary exercise. Cardiopulmonary exercise testing will include a 20 W initial steady phase during which RHC numbers will be recorded and echocardiogram with liver blood flow will be obtained. This will take up to 7 minutes followed by quick (every 1 minute increase in 20W) ramp to peak exercise. At peak exercise repeat hemodynamics and echocardiography will be obtained.

Subjects will further be monitored with:

[figure not shown]
- Telemetry (SOC)
- ClearSite/CheetahMedical/Sphygmocor/ReDS for continuous non-invasive hemodynamic/lung fluid content recording (CS)
- Continuous urine output (ml/hour) recording if foley is present (SOC)
- A non-invasive wrist monitor/chest band to monitor the heart rate variability

Baseline hemodynamics and exercise CPX will be performed before and after the nerve block detailed below.

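### Section 14 names only independent-group tests for categorical outcomes in a one-arm before-after trial, and no paired method for categorical or ordinal change (minor)

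*Combined protocol and SAP*

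**What the plan says.** Section 4 describes the design: "This study will be a prospective, uncontrolled clinical trial". Each subject is his or her own comparison: "Baseline hemodynamics and exercise CPX will be performed before and after the nerve block detailed below".

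Section 14 sets the tests. It begins "Statistical comparisons will be made using t-tests for continuous outcomes and chi square" and completes the categorical part as "chi square or Fisher's exact test (depending on overall event rates) for categorical outcomes". The next sentence brings in pairing, for one test only: "Paired t-tests will be used to compare changes from baseline to post-intervention". The significance level is then linked to within-subject change: "a two-sided 0.05 level of significance will be used to declare change in pre- and post-procedure variables different". No McNemar, signed-rank or marginal-homogeneity test appears anywhere in the document.

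The outcome most exposed is dyspnea. It is the third objective in section 2 and a secondary efficacy endpoint at the end of section 4. The instrument is listed as "Dyspnea questionnaire using a 7-point Likert scale and Visual Analog Scale (CS". The study events table schedules it at baseline, post block, recovery, 24 h and 48 h.

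The only two independent groups in the document are the enrolment targets in section 7: 15 subjects with preserved and 15 with reduced ejection fraction, up to 30 in all. No objective, endpoint or analysis sentence compares them.

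**The concern.** Chi-square and Fisher's exact test take the two columns of the table to be different people. In this trial, a before-after table would hold the same people twice. The tests use only the two marginal counts. They discard how many subjects changed in each direction, which is the information that bears on a treatment effect.

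If a subject's two answers are positively correlated, as is usual for symptoms, these tests overstate the standard error of the change. They then reject too rarely under the null and can miss a real change. In a trial of at most 30 subjects with symptom relief as a stated objective, that loss is worth avoiding when it costs nothing to do so.

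**Working it through.** **The plan's own figure.** There is none for a categorical outcome. The only power statement (16 subjects, power 0.90) concerns central venous pressure, a continuous variable: "Based on preliminary animal experiments, we anticipate a reduction of CVP of 25"%. It gives no standard deviation and has no bearing here. What follows illustrates the consequence if the named tests were used on paired data.

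**Inputs.** From the documents: n = 30 (section 7, upper target) and two-sided 0.05 (section 14). Assumed, because the documents give neither: the before and after rates p1 and p2, and the within-subject correlation ρ.

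**Step 1, the cause.** For the difference in proportions:
- variance if treated as independent = [p1(1−p1) + p2(1−p2)]/n
- true paired variance = the same minus 2ρ√[p1(1−p1)p2(1−p2)]/n

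With p1 = p2 = 0.5 the ratio of the two is 1/(1−ρ). At ρ = 0.5 the standard error is inflated by √2 = 1.414, so the effective critical value is 1.96 × 1.414 = 2.77. Its two-sided normal tail is about 0.006.

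**Step 2, exact enumeration.** The cell probabilities are p11 = p1p2 + ρ√[p1(1−p1)p2(1−p2)], p10 = p1 − p11, p01 = p2 − p11 and p00 = 1 − p11 − p10 − p01. For 0.50 to 0.25 with ρ = 0.5 they are 0.233, 0.267, 0.017 and 0.483. All multinomial outcomes for n = 30 are summed.
- Fisher and uncorrected chi-square are applied to the margins as if they came from two groups of 30.
- Exact McNemar uses the b and c discordant pairs: p = 2·P(X ≤ min(b,c)), with X ~ Bin(b+c, ½), capped at 1.
- Mid-p McNemar subtracts P(X = min(b,c)) from that p-value (and is set to 1 when b = c).

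Actual type I error, 50% at both times:

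| ρ | Fisher | Chi-square | Exact McNemar |
|---|---|---|---|
| 0.5 | 0.002 | 0.006 | 0.018 |
| 0.3 | 0.009 | 0.020 | 0.023 |
| 0 | 0.027 | 0.052 | 0.028 |
| −0.3 | 0.053 | 0.089 | 0.030 |

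The chi-square value at ρ = 0.5 agrees with the hand calculation in step 1.

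Power, 50% falling to 25%:

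| ρ | Fisher | Chi-square | Exact McNemar | Mid-p McNemar |
|---|---|---|---|---|
| 0.5 | 0.37 | 0.52 | 0.70 | 0.81 |
| 0.3 | 0.40 | 0.52 | 0.54 | 0.64 |
| 0.2 | 0.40 | 0.52 | 0.48 | 0.58 |

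A second pair of rates, 60% falling to 30%, gives Fisher 0.57, chi-square 0.72 and exact McNemar 0.88 at ρ = 0.5. At ρ = 0.3 it gives 0.57, 0.69 and 0.70.

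**Step 3, which named test would apply.** The plan chooses between the two by overall event rate. For 50% and 25% the pooled rate is 37.5%, so the expected counts are 30 × 0.375 = 11.25 events and 18.75 non-events per column. Chi-square would normally be chosen, so its column is the fairer comparison for these rates. Fisher's column matters for rarer outcomes.

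**The case against.** The strongest reply is that section 14 never says chi-square or Fisher will be applied to before-after categories. It gives a generic list of tests that also includes unpaired t-tests, then treats baseline-to-post change in a separate, paired sentence. On that reading the list is for between-group comparisons, and the two ejection-fraction groups would suit it. This stands in part. A reader might infer that the plan commits to analysing paired categories as independent groups, but the text does not go that far. It leaves the purpose of these tests unstated. Even on the charitable reading no paired categorical method is named, and the between-group comparison that would justify the list is not described.

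Second, few outcomes are exposed. The efficacy endpoints are almost all continuous. The Visual Analog Scale is covered by the paired t-test, and the Likert score could be analysed as a number in the same way. A reader might add bendopnea and orthostatic hypotension as paired yes/no outcomes, but the documents do not support either. Bendopnea has no stated post-block repeat and is not an endpoint. Orthostatic vitals are repeated, but orthostatic hypotension is listed only as a side effect, with no before-after test planned. This objection stands and limits the point to the dyspnea item and any dichotomy derived later.

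Third, the power loss depends on the assumptions. Against chi-square, exact McNemar gains 18 points at correlation 0.5 and 2 points at 0.3, and loses 4 points at 0.2. The illustration uses a yes/no outcome, so it does not measure any loss on the 7-point score itself. This also stands.

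**Conclusion.** The gap is real and minor. Section 14 names only independent-group tests for categorical outcomes and confines pairing to t-tests, in a trial whose stated comparisons are within subject. If those tests were applied to a before-after categorical outcome, such as the 7-point dyspnea item treated as categories, the error rate would be wrong. With positive within-subject correlation it would be conservative. With 50% at both times, 30 subjects and correlation 0.5, actual type I error would be 0.2% for Fisher and 0.6% for chi-square, not 5%. The power cost against exact McNemar runs from substantial at correlation 0.5 to none against chi-square at 0.2. All of this rests on assumed rates and correlations.

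A reader might infer a risk of false-positive claims, but the calculation shows material inflation only for chi-square under negative correlation (8.9% at −0.3), which is not the usual pattern for repeated symptom reports. A reader might also infer that the main result is compromised. It is not, because the primary endpoints are continuous pressures and no primary endpoint is affected.

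**What to change.** In section 14:
- Restrict chi-square and Fisher's exact test to comparisons between independent groups (preserved versus reduced ejection fraction), and say whether such a comparison will be made.
- For within-subject change in a yes/no outcome, name the McNemar test, exact or mid-p (chosen in advance), with a confidence interval for the paired difference in proportions.
- State how the 7-point Likert dyspnea score will be treated, and name a paired method for it, such as the Wilcoxon signed-rank test.

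The cost is a sentence or two of text, settled before the data are analysed. It needs no extra data, visits or subjects.

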### **2. Purpose of the Study:**

Splanchnic vasoconstriction may contribute to decompensation of chronic heart failure via volume redistribution from the splanchnic vascular bed to the central compartment. This is a sympathetically mediated reflex and can be interrupted through a splanchnic nerve block. Therefore, we hypothesize that interruption of the efferent/afferent innervation of the splanchnic vasculature will decrease cardiac congestion and improve renal function in subjects presenting with heart failure.

Objectives:

1. We will determine if splanchnic nerve blockade decreases cardiac preload as measured by invasive hemodynamics.
2. We will determine if splanchnic nerve blockade will improve invasive hemodynamics during exercise.
3. We will determine if splanchnic nerve blockade improves symptoms of shortness of breath.

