- Increase in cardiac output at rest, improvement in echocardiographic parameters like ejection fraction (increase), central venous pressure (decrease), pulmonary artery systolic pressure (decrease), right ventricular diameter (decrease), left ventricular diameter (decrease)
- Reduction in pro brain natriuretic peptide (pro-BNP)
- Increase in UOP (output measured in ml/hour) and renal function (BUN and creatinine) in the hours following the procedure.

- Symptomatic improvement like a decrease in dyspnea (dyspnea questionnaire) and 6-minute walk test

Exploratory aims:

- Change in cardiac and autonomic markers after nerve block (i.e. angiotensin and catecholamines)

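### Section 14 lets each of the 12 to 13 non-catheter secondary variables be declared changed at its own two-sided 0.05, with no testing order, adjustment or descriptive label

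*Combined protocol and SAP*

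**What the plan says.** Section 14 (Data Analysis & Statistical Considerations) sets both the test and the decision rule. On the test: "Paired t-tests will be used to compare changes from baseline to post-intervention". On the rule, as the default wherever nothing different is stated: "a two-sided 0.05 level of significance will be used to declare change in pre- and post-procedure variables different". Nothing different is stated anywhere for the secondary variables: there is no hierarchy, gatekeeping, alpha split or adjustment.

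The efficacy endpoint list in section 4 has primary, secondary and exploratory tiers. Apart from the resting catheter pressures, which also appear as primary, the secondary tier contains:

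- for cardiac function, "Increase in cardiac output at rest, improvement in echocardiographic parameters like ejection fraction (increase), central venous pressure (decrease), pulmonary artery systolic pressure (decrease"), plus the diameters of both ventricles;
- the pro-BNP level;
- for the kidney, "Increase in UOP (output measured in ml/hour) and renal function (BUN and creatinine) in the hours following the procedure";
- for symptoms, the dyspnea score and the distance walked in six minutes.

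The exploratory tier holds only cardiac and autonomic markers, with angiotensin and catecholamines as examples.

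Objective 3 in section 2 reads "We will determine if splanchnic nerve blockade improves symptoms of shortness of breath". Section 4 describes the instrument as "Dyspnea questionnaire using a 7-point Likert scale and Visual Analog Scale (CS"). The study events table schedules it at four points after the block: post-block, recovery, 24 h and 48 h. The follow-up text in the same section mentions only after the block and 48 h. No scale or time is designated for the analysis.

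**The concern.** The wording of section 14 is a rule for declaring a change, not a description of how p-values will be displayed. Applied as written, it lets the trial declare a symptom, biomarker, renal or echocardiographic effect from whichever secondary test falls below 0.05, whatever the primary result. The 0.05 holds for each variable separately. It does not hold for a conclusion drawn from the smallest of a dozen p-values.

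Dyspnea is the clearest case. The protocol says it will settle whether shortness of breath improves, but up to eight scale-by-time combinations could answer that question. Section 4 justifies the lack of a control group by the invasive hemodynamic measurements. That argument does not extend to self-reported symptoms.

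**Working it through.** **The plan's own figure.** None exists for the secondary family. The only Type I error tied to a named test is the 0.05 in section 14's power statement, which concerns central venous pressure. What follows therefore measures what the rule implies; it does not check a stated family-wise rate.

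**Inputs from the documents.**
- Level: 0.05, two-sided, per variable (section 14).
- Test: paired t-test (section 14).
- Sample size: 16 (power statement) or up to 30 (enrolment target, section 7).
- Count: cardiac output 1, echocardiographic parameters 5, pro-BNP 1, urine output, BUN and creatinine 3, dyspnea 1, 6-minute walk 1. That is 1 + 5 + 1 + 3 + 1 + 1 = 12, or 13 with Likert and VAS tested separately at one time.
- Dyspnea family: 2 scales × 4 post-block times = 8.

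**Input assumed.** The documents give no correlation between changes, so a common correlation r from 0 to 0.8 is used.

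**Independent tests (r = 0).** P(at least one p<0.05) = 1 − 0.95^k:
- k = 12: 1 − 0.95^12 = 0.460
- k = 13: 1 − 0.95^13 = 0.487
- k = 8: 1 − 0.95^8 = 0.337

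In the favourable direction only, each test has nominal error 0.025, so for k = 13 the chance is 1 − 0.975^13 = 0.281.

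**Correlated tests.** Simulation of normally distributed changes with mean zero, paired t-tests, n = 16, 40,000 replicates per cell. Results at n = 30 agree to within about 0.01.

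| Family | r = 0 | r = 0.3 | r = 0.5 | r = 0.8 |
|---|---|---|---|---|
| 13 tests, either direction | 0.48–0.49 | 0.43 | 0.345 | 0.20–0.21 |
| 12 tests, either direction | 0.46 | 0.405 | 0.33 | 0.195 |
| 13 tests, favourable direction | 0.28 | 0.22 | 0.17–0.18 | 0.10 |
| 8 dyspnea tests, either direction | 0.34 | 0.31 | 0.26 | 0.165 |

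Grouping the 13 tests by domain, with higher correlation within than between domains, gives 0.35 to 0.47 in either direction. At r = 0.9 the 13-test figure is still about 0.14.

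**Plausible correlation for dyspnea.** Changes at different times share one baseline. With equal variance v and equal pairwise covariance c, two such changes have covariance v − c and variance 2v − 2c, so their correlation is (v − c)/(2v − 2c) = 0.5. The two scales also measure the same symptom. Correlations of 0.5 to 0.8 are therefore more credible than 0, which puts the eight-test figure at about 0.16 to 0.26.

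**The case against.** The strongest reply is that this is an uncontrolled physiological study of up to 30 subjects. Its endpoints are already tiered, and it promises 0.05 per variable and nothing more. Many such studies leave secondaries unadjusted and treat them as descriptive. The reply stands in part: no stated error rate is breached, and a full multiplicity scheme over 13 variables would be out of proportion. But the plan does not call the secondaries descriptive. It says changes will be declared, and it keeps the exploratory label for other variables.

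Four stronger readings are tempting, and the documents do not support them.

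- A reader might infer a fixed one-in-three chance of a false secondary benefit. That figure needs a correlation near 0.5, which the documents do not supply, and it counts changes in the harmful direction. Counting favourable changes only, 13 tests do not reach one in three even if independent (0.28).
- A reader might infer that a promised 0.05 family-wise rate is exceeded several-fold. No such rate is promised for the secondaries.
- A reader might infer that renal benefit may be claimed from any one of urine output, BUN or creatinine. The list joins these with a plain conjunction; the and/or wording is used only for the catheter pressures. Section 12 names urine output as the measure of renal function, and renal function is not one of the three numbered objectives.
- A reader might equate these figures with the error rate of an ineffective block. The calculation assumes no mean change. With repeat exercise, elapsed time, a held morning diuretic and no control group, changes can arise without any block effect.

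**Conclusion.** The concern holds in limited form. Section 14 allows each of 12 to 13 non-catheter secondaries to be declared changed at full 0.05, with no order, adjustment or descriptive label. If no secondary truly changes, the chance of at least one p<0.05 is about 20% to 49% in either direction, or 10% to 28% in the favourable direction against 2.5% for a single test. For dyspnea it is 16% to 34% if all eight combinations are tested, and more plausibly 16% to 26%.

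The ranges rest on an assumed common correlation of 0 to 0.8, on normally distributed changes, and for dyspnea on every scheduled combination being tested. The conclusion does not depend on choosing 12 or 13 tests, or 16 or 30 subjects. The point should be corrected before analysis. It does not affect the primary comparison.

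**What to change.** In section 14, limit the rule for declaring a difference at 0.05 to two places:

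1. The primary endpoint, once the documents agree on what it is. The efficacy list gives exercise pulmonary artery mean and wedge pressures together with resting pressures, whereas the power statement names central venous pressure.
2. For objective 3, one dyspnea scale at one post-block time, both fixed before analysis.

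Then add wording such as: All other secondary variables, including the remaining dyspnea scale and times, are reported as mean change with a 95% confidence interval; their p-values are unadjusted and descriptive, and no claim of effect rests on them.

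If the sponsor also wants a formal renal claim, urine output (the measure section 12 names) can be tested with the chosen dyspnea measure by Holm at overall two-sided 0.05. The smaller p-value is then compared with 0.05/2 = 0.025 and, if it passes, the other with 0.05.

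The cost is a few sentences, with no new data or subjects. The downside is that the remaining secondaries can no longer be declared positive on their own. If Holm is used, one of the two tested measures must reach 0.025. The change limits chance findings only; it does not remove time, repeat-exercise or held-diuretic effects in this uncontrolled design.

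### The only power statement describes a two-group test that this uncontrolled, paired trial does not have, gives no SD, and covers only part of the primary endpoints

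*Combined protocol and SAP*

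**What the plan says.** **Design and test.** Section 4 states: "This study will be a prospective, uncontrolled clinical trial". Section 14 says: "Paired t-tests will be used to compare changes from baseline to post-intervention", with a two-sided 0.05 level by default.

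**Power.** Section 14 says: "For a sample size of 16, If the true difference in the experimental and control means is 25%, we will be able to reject". What would be rejected is a statement about two groups: "the population means of the experimental and control groups are equal with probability (power) .90", at a Type I error of 0.05. On the effect: "Based on preliminary animal experiments, we anticipate a reduction of CVP of 25" percent. No SD, SD of change or pre/post correlation appears in the text, and 16 is not identified as pairs, total or per group.

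**Endpoint.** For the power analysis, "our primary endpoint is decreased in central venous pressure following nerve blockade". The efficacy endpoint list at the end of section 4 has two primary items:
- (a) PA mean and wedge pressure at 20 W and at peak exercise;
- (b) CVP, diastolic PA pressure and wedge pressure, joined by and/or, at 30 minutes after the block.

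Item (b) is then repeated word for word as secondary. Item (a) corresponds to the second objective in section 2: "We will determine if splanchnic nerve blockade will improve invasive hemodynamics during exercise".

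**Numbers.** Section 7 sets a target of up to 30 subjects, 15 with preserved and 15 with reduced ejection fraction.

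**Block success.** Section 14 adds: "Procedural success to block the splanchnic nerves will be assumed in 70% of the cases". It also notes that technical success cannot be measured directly.

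**The concern.** The power figure is the only quantitative support for the size of an invasive study, and it does not describe that study. The hypothesis it names compares two groups, whereas the trial measures the same subjects before and after a block. A paired test depends on the SD of the within-subject change. A two-group test depends on the between-subject SD. The same 0.90 therefore carries different assumptions depending on which was meant.

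The endpoint matters as much. Section 14 and the endpoint list do not agree on what decides the trial, and the first-listed primary item has no stated effect size or power. A reader cannot tell what change the primary endpoint can detect, or how many pairs the conclusion rests on.

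**Working it through.** **Inputs from section 14:** n = 16, a 25% fall in CVP, power 0.90, alpha 0.05, two-sided paired t-test. **Input from section 7:** up to 30, or 15 per phenotype. **Not given:** any SD. Below, SDs are percentages of mean baseline CVP, because the effect is given only as a percentage.

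**1. Trying to reproduce 0.90.** For n pairs, with d = mean change / SD of change, power is the probability that a noncentral t with n − 1 degrees of freedom and noncentrality d√n exceeds the two-sided 5% critical value in absolute terms. For two groups of m, the degrees of freedom are 2m − 2 and the noncentrality is d√(m/2), with d based on the between-subject SD. Without an SD the sum only runs backwards, to the SD that would give 0.90:

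| Reading of 16 | d needed | SD needed = 25/d |
|---|---|---|
| 16 pairs | 0.868 | 28.8 (SD of change) |
| 16 per group | 1.185 | 21.1 (between-subject) |
| 8 per group | 1.745 | 14.3 (between-subject) |

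Each reading reaches 0.90 with a different SD, so the figure cannot be checked. If the relevant SD is assumed to be 25%, the three readings give 0.96, 0.78 and 0.46.

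**2. What the planned paired test can detect with power 0.90.**

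| Pairs | Detectable d | Largest SD of change for a 25% fall |
|---|---|---|
| 15 | 0.901 | 25/0.901 = 27.8% |
| 16 | 0.868 | 25/0.868 = 28.8% |
| 30 | 0.612 | 25/0.612 = 40.8% |

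For assumed SDs of change of 25%, 35% and 50%, power is 0.96, 0.76 and 0.465 at 16 pairs, and above 0.99, 0.97 and 0.75 at 30. These SDs are illustrations, not values from the documents.

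**3. Endpoints.** CVP appears only as one of three components of primary item (b). Item (a), the exercise pressures, has no effect size or SD in the text, so no power can be computed for it.

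**4. How 16 relates to 30.** Section 9 counts a subject as enrolled at signed consent, before the hemodynamic exclusions. On that reading, 30 − 16 = 14 consented subjects could be lost before fewer than 16 pairs remain. Section 7, however, says the study enrols those who meet the criteria, and those criteria include the hemodynamic one. Section 4 classes subjects stopped on hemodynamic grounds as screen failures and discards their data. On that second reading, such exclusions do not reduce the 30.

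**5. Block success, as an illustration only.** Suppose both the 25% and the SD of 28.8% refer to successful blocks, and failed blocks have no effect. The mean change is 0.70 × 25 = 17.5. The variance of change is 28.8² + 0.70 × 0.30 × 25² = about 830 + 131.25, so the SD is about 31.0 and d = 17.5/31.0 = 0.564. Power is then about 0.56 at 16 pairs and 0.85 at 30. If 25% is already the average over all attempted blocks, there is no such loss.

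**The case against.** The strongest reply is that the two-group sentence is loose wording for post versus pre. The planned analysis is stated correctly, resting CVP is a named component of a primary item, and a ceiling of 30 comfortably exceeds 16. All of that stands. On its own the wording would be a small repair. What remains is the absence of an SD under any reading, and the disagreement over which endpoint is primary.

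A second reply is that pilot pressures may be in Figure 1, Panel C, which is not visible here. That is possible. But section 3 describes the pilot as resting pressures in acute heart failure, the power paragraph cites animal experiments instead, and the design and endpoint mismatches would remain.

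Several stronger conclusions are tempting, and the documents do not support them:
- **That the trial is underpowered, or 0.90 is wrong.** Without an SD neither can be shown.
- **That 16 contradicts 30.** A ceiling above 16 only raises power for a pooled paired test. What is missing is the link between the two numbers.
- **That screen failures will erode the 30.** The text supports both readings of enrolment, and no screen-failure rate is given.
- **That 70% block success cuts power to 0.56.** This needs the effect and the SD both to refer to successful blocks alone, which is not stated.

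**Conclusion.** The point holds as an inconsistency that should be fixed. The stated power belongs to a test the design does not contain, cannot be reproduced, and addresses one component of one of the two primary items. These findings rest on the text alone. The size of any power shortfall is unknown. The firm numbers are conditional ones: a 25% fall has 0.90 power in a paired test only if the SD of change is at most 28.8% of baseline at 16 pairs, or 40.8% at 30. They assume a two-sided 0.05 level and approximately normal changes. No figure can be given for the exercise endpoints.

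**What to change.** 1. Reconcile section 14 with the efficacy endpoint list so that both name the same primary endpoint or endpoints, and list the resting item once. The choice is the sponsor's.
2. Replace the two-group sentence with a paired calculation for that choice, at the expected number of evaluable pairs. Give the mean change and the SD of change with its source, both as a percentage of mean baseline if the effect stays a percentage. If the pilot supplies the SD, label it as resting pressures in acute heart failure. If no SD is defensible, report the detectable standardised changes in the second table above instead.
3. State whether the assumed change is averaged over all attempted blocks. Only if the effect and the SD both refer to successful blocks, with no effect in failures, use 0.70 times the effect and add 0.21 times the effect squared to the variance. Do not apply this to a mean or SD taken from all attempted blocks, such as the pilot's, because any failures are already in those figures.
4. Say how 16 relates to the target of up to 30 and whether hemodynamic screen failures count toward it, or delete 16.

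The cost is one rewritten paragraph and a substantive decision on the primary endpoint. The restated power may be less favourable than 0.90. No added patients are needed to restate it.
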